TITLE: A comparison of Oral VTS-K (combination of VTS-Aspirin and oral ketamine) to Nurtec (Rimegepant) for managing acute headache in the ED: randomized, open-label, clinical trial.

NCT#:

Document Date: March 23, 2021

TITLE: A comparison of Oral VTS-K (combination of VTS-Aspirin and oral ketamine) to Nurtec (Rimegepant) for managing acute headache in the ED: randomized, open-label, clinical trial.

INTRODUCTION

Headaches affect over 50% of patients annually, with close to 4% of ED visits for headache. Most headaches managed in the ED are benign, with 90% of these headaches classified as tension, migraine, or cluster. At present, the satisfaction with ED treatment of headache is low, and despite the multitude of available medications, the evidence- based treatment options are often quite limited. There are over twenty different types of medications available to the ED clinicians for managing headache, many with different routes of administration (parenteral, intranasal, subcutaneous, and oral). Many of these medications are provided in so-called “headache cocktail”, which varies based on the physician, institution, and patient preferences.

STUDY OBJECTIVES

To compare analgesic efficacy and rates of side effects of a proprietary formulation of orally administered aspirin and ketamine (AOK) to a Nurtec ODT (Rimegepant) for pain management in adult ED patients presenting to the ED with acute headache.

HYPOTHESIS

We hypothesize that the administration of AOK will provide similar analgesia at 60 minutes post-administration in comparison to Nurtec (Rimegepant) in adult patients presenting to the ED with acute headache. The primary outcome of this trial is the difference in participant’s pain scores at 60 minutes post-medication administration.

STUDY DESIGN

Subjects: Patients 18 years of age and older presenting to the ED with acute headache (defined as HA lasting no more than 1 week) and an initial pain score of 5 or more on a standard 11- point (0 to 10) numeric rating scale and requiring oral analgesia as determined by the treating attending physician. Patients’ screening and enrollment will be performed by study investigators and research assistants. All patients will be enrolled at various times of the day when study investigators will be available for patient enrollment and an ED pharmacist will be available for medication preparation.

Eligibility Criteria: Patients 18 years of age and older presenting to the ED with acute headache (<7 days) and an initial pain score of 5 on a standard 11-point (0 to 10) numeric rating scale. Patients will have to be awake, alert, and oriented to person, place, and time, and will be able to demonstrate understanding of the informed consent process and content. Patients also will have to demonstrate ability to verbalize the nature of any adverse effects they might experience as well as to express their pain severity by using the NRS.

Exclusion Criteria: Patients with altered mental status, allergy to aspirin, ketamine, rimegepant, pregnant patients, unstable vital signs (systolic blood pressure <90 or >180 mm Hg, pulse rate <50 or >150 beats/min, and respiration rate <10 or >30 breaths/min), inability to provide consent, consumption of Aspirin/NSAID's within 6 hours of arrival to the ED, or acetaminophen within 4 hours of arrival to the ED, active PUD, history of GI Hemorrhage, history of renal and hepatic insufficiency, past medical history of alcohol or drug abuse, or schizophrenia, as well as clinical findings concerning for acute intracranial process, acute infections process, or vascular catastrophe, pregnant patients and breastfeeding patients.

Design: This is a prospective, randomized, open-label, equivalence trial comparing analgesic efficacy and safety of AOK and Nurtec (Rimegepant) in patients presenting to the ED of Maimonides Medical Center with acute headache. Upon meeting the eligibility criteria, patients will be randomized into one of the two study arms: Group I will receive AOK, and Group II will receive Nurtec

Data Collection Procedures: Each patient will be approached by a study investigator for acquisition of written informed consent and Health Insurance Portability and Accountability Act authorization after being evaluated by the treating emergency physician and determined to meet study eligibility criteria. When English will not be the participant's primary language, a language-appropriate consent form will be used and non-investigator, hospital-employed, trained interpreters or licensed telephone interpreter will assist in acquisition of informed consent. Baseline pain score will be determined with an 11-point numeric rating scale (0 to 10), described to the patient as "no pain" being 0 and "the worst pain imaginable" being 10. A study investigator will record the patient's body weight and baseline vital signs. All data will be recorded on data collection sheets, including patients' sex, demographics, medical history, and vital signs, and entered into SPSS (version 24.0; IBM Corp) by the research manager. Confirmation of written consent acquisition for all participants, and statistical analyses will be conducted by the statistician, who will work independently of any data collection.

Data Analysis: Data analyses will include frequency distributions and independent-sample t-test to assess differences in pain scores at the various intervals. Mixed-model linear regression will be used to compare changes in pain numeric rating scale across time points. For categorical outcomes (eg, complete resolution of pain), a χ^2 or Fisher's exact test will be used to compare outcomes at 60 and 120 minutes. Based on the validation of a verbally administered rating scale of acute pain in the ED and the comparison of verbal and visual pain scales, we will use a primary outcome consisting of a minimal clinically meaningful difference of 2 points between two groups at the 60-minute and 120-minute pain assessment.^{28,29}

Sample Size: Assuming the minimum statistically significant difference of 2 points on NRS, with Standard deviation of 3.0, alpha=0.05, and power of 80%, the sample size will require 40 patients per group. To account for potential loss to follow up (discharge from the ED before 120 minutes), we will enroll 45 patients in each group.

Expected Outcomes: The primary outcome will include a comparative reduction of pain scores on numeric rating pain scale (NRS) at 60 minutes from the baseline. The secondary outcomes will include a need for rescue analgesia, rates of adverse effects, and change in pain score up to 120 minutes.

Adverse Events:

With respect to unique adverse effects of ketamine, we will use Side Effect Rating Scale for Dissociative Anesthetics (SERSDA) and Richmond Agitation Sedation Scale (RASS) (ref) SERSDA Scale includes fatigue, dizziness, nausea, headache, feeling of unreality, changes in hearing, mood change, general discomfort, and hallucinations with severity of each graded by patients on a five-point scale, with “0” representing the absence of any adverse effects and “4” representing a severely bothersome side effect. RASS evaluates the severity of agitation and/or sedation in accordance with the nine-point scale with scores ranging from “-4” (deeply sedated) to “0” (alert and calm) to “+4” (combative).

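### The equivalence label can be read to cover safety, but the plan has no margin or interval rule for adverse-effect rates, and a test of difference cannot supply one

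*Combined protocol and SAP*

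**What the plan says.** The Design paragraph calls the study an "equivalence trial comparing analgesic efficacy and safety of AOK and Nurtec (Rimegepant"). The other sections bear on safety as follows.

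- **Hypothesis:** similarity is proposed for pain relief only: "AOK will provide similar analgesia at 60 minutes post-administration in comparison to Nurtec (Rimegepant"). There is no matching hypothesis for safety.
- **Study Objectives:** the aim is "To compare analgesic efficacy and rates of side effects", which is a neutral comparison.
- **Expected Outcomes:** "The secondary outcomes will include a need for rescue analgesia, rates of adverse effects, and change in pain score up to 120 minutes". Adverse effects and rescue use are therefore secondary.
- **Sample Size:** the calculation begins "Assuming the minimum statistically significant difference of 2 points on NRS" and uses no event rate. It arrives at 40 per group, with 45 enrolled.
- **Data Analysis:** "For categorical outcomes (eg, complete resolution of pain), a χ^2 or Fisher's exact test will be used to compare outcomes" at 60 and 120 minutes. Adverse effects and rescue use are not named there.
- **Adverse Events:** SERSDA and RASS will be collected. No score is said to count as an event, and no assessment time or between-group comparison is given.

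No section states a margin for a difference in rates, or says how a conclusion about safety will be reached.

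**The concern.** Equivalence is shown when a confidence interval for the difference lies inside a margin fixed in advance. The plan's only threshold, 2 points on the pain scale, cannot be applied to a proportion. If the label includes safety, the plan has no means of testing that part of it. If it does not, the sentence needs to say so.

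What is at stake is the statement about harm at the end of the trial. Ketamine-specific effects are expected enough for the plan to collect two dedicated scales. A chi-square or Fisher result with p above 0.05, in a trial carrying this label and with no interval beside it, would leave the reader unable to tell a small difference from a large one estimated imprecisely.

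**Working it through.** **1. The plan's own figure.** The inputs, from Sample Size, are a difference of 2, SD 3.0, alpha 0.05 and power 80%.

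- Two-sided test of difference: 2 × 3² × (1.960 + 0.842)² / 2² = 35.3, so 36 per group (37 by the t calculation).
- Equivalence by two one-sided tests, margin 2, true difference 0, 5% per side: 2 × 3² × (1.645 + 1.282)² / 2² = 38.6, so 39 per group. By the t calculation it is 40, with 81.0% power.

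The stated 40 matches the second calculation. Enrolment of 45 fits 40 / 0.90 = 44.4 rounded up, although no loss rate is given. On either route the size is set by pain alone.

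**2. Assumptions for safety.** The documents give no adverse-effect or rescue rate and no margin, so both are varied below, with 45 per arm.

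**3. Precision and attainable margin.** With a common true rate p, the standard error is SE = √(2p(1−p)/45). The 95% half-width is 1.96 × SE. The smallest margin giving 80% power for equivalence (one-sided 5% each, equal true rates) is (1.645 + 1.282) × SE.

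| Rate p | SE | 95% half-width (points) | Smallest margin (points) |
|---|---|---|---|
| 5% | 0.046 | 9 | 13 |
| 10% | 0.063 | 12 | 19 |
| 20% | 0.084 | 17 | 25 |
| 30% | 0.097 | 19 | 28 |
| 50% | 0.105 | 21 | 31 |

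These are normal approximations, and rough at 5%, where only 45 × 0.05 = 2.25 events per arm are expected. Exact binomial enumeration of the equivalence test (90% Wald interval inside the margin) gives the same picture:

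- 15-point margin: power 87% at a 5% rate, 54% at 10%, 13% at 20%.
- 20-point margin: 86% at 10%, 54% at 20%, 33% at 30%.
- 10-point margin: 42% at 5%, 9% at 10%, about 0% from 20% upward.

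**4. Power of the tests of difference.** Exact enumeration, two-sided 5%, chi-square uncorrected:

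| True rates | Fisher | Chi-square |
|---|---|---|
| 10% v 20% | 18% | 28% |
| 20% v 40% | 46% | 56% |
| 30% v 50% | 41% | 49% |
| 10% v 30% | 57% | 69% |
| 5% v 25% | 71% | 81% |
| 20% v 50% | 82% | 87% |

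A true doubling from 20% to 40% is thus missed in 54% of trials with Fisher and 44% with chi-square.

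**5. One illustrative result.** Suppose 18/45 on AOK and 10/45 on rimegepant. Fisher gives p = 0.11 and chi-square p = 0.069. The risk difference is 0.400 − 0.222 = 0.178, with Newcombe 95% interval −1 to +35 points. Both tests are non-significant, while the data remain compatible with an excess of about 35 points.

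**The case against.** The strongest reply is that the Design sentence is ambiguous. Equivalence may describe the trial through its primary hypothesis, with efficacy and safety merely listed as what is compared. The hypothesis, the objective, the secondary status of adverse effects and the sizing all fit that reading. This stands: a reader might infer that the sponsor has declared safety equivalence as an aim, but the documents do not settle it.

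Four further points limit the concern.

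- A reader might infer that a non-significant safety test will be reported as equal safety. No section says so; the plan is silent on how safety will be concluded.
- A reader might infer that any large excess would usually be missed. That depends on the rates and the test: 5% against 25% is detected in 71% to 81% of trials.
- A reader might infer that 45 per arm could meet no useful margin for safety. The documents do not say what margin would be useful, and equivalence power exceeds 85% at a 5% rate with a 15-point margin or a 10% rate with a 20-point margin.
- Applying chi-square or Fisher to adverse effects is an inference, since the plan's example is resolution of pain. It is a fair one. If it is wrong, safety has no planned comparison beyond frequency distributions.

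It is also true that low power for secondary safety outcomes is ordinary in a trial sized on efficacy, and that pain itself is assigned a t-test with no stated equivalence rule. Repairing the pain analysis would still leave safety without a margin or an interval.

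**Conclusion.** The point holds as a mismatch between label and method. The design label can be read to include safety, and the plan contains nothing that could show equivalent safety. That part needs no assumed rates, because a non-significant test of difference does not establish equivalence at any sample size.

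The size of the problem does rest on assumed rates and 45 evaluable patients per arm. Equivalence could be shown with 80% power only for uncommon events or with wide margins. For event rates of 20% or more the margin would have to be about 25 points or wider, and a non-significant comparison would often leave a sizeable excess on AOK unexcluded. This is a matter of wording and reporting that should be settled before analysis; it does not call the sample size for pain into question.

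**What to change.** - **Design:** limit equivalence to pain at 60 minutes, in line with the Hypothesis, and describe safety and rescue use as estimated.
- **Data Analysis:** name adverse effects and rescue use explicitly. Report each rate as a risk difference (AOK minus rimegepant) with a 95% confidence interval by the Newcombe or Miettinen-Nurminen method. For SERSDA and RASS, first state what score at what time counts as an event.
- **Data Analysis, added sentence:** a non-significant chi-square or Fisher result will not be reported as similar or equivalent safety; the upper confidence limit for the excess on AOK will be given.

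The cost is wording and one interval per table row, with no extra patients. The downside is that the sponsor gives up any safety-equivalence statement. Keeping one would require a justified margin and a size to match. From n = 2p(1−p)(1.645 + 1.282)²/margin², a 10-point margin needs 155 per arm at a 10% rate and 275 at 20%.

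### Declared an equivalence trial, but no equivalence margin is designated, no rule says what result shows equivalence, and the named test looks for differences

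*Combined protocol and SAP*

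**What the plan says.** All references are to the combined protocol and SAP.

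- **Design:** "This is a prospective, randomized, open-label, equivalence trial comparing analgesic efficacy and safety of AOK and Nurtec (Rimegepant").
- **Hypothesis:** "administration of AOK will provide similar analgesia at 60 minutes post-administration", compared with Nurtec. How close counts as similar is not quantified.
- **Data Analysis, pain scores:** an "independent-sample t-test to assess differences in pain scores at the various intervals", and "Mixed-model linear regression will be used to compare changes in pain numeric rating scale across time points". No between-arm contrast or test is named for the model. Chi-square and Fisher's exact tests are reserved for categorical outcomes.
- **Data Analysis, threshold:** a "primary outcome consisting of a minimal clinically meaningful difference of 2 points between two groups at the 60-minute and 120-minute pain assessment".
- **Sample Size:** "Assuming the minimum statistically significant difference of 2 points on NRS, with Standard deviation of 3.0, alpha=0.05, and power of 80"%, giving 40 per group; allowing for losses, "we will enroll 45 patients in each group".

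No section designates a margin, mentions two one-sided tests or a confidence interval, gives the sidedness of alpha, or says what result would establish equivalence.

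**The concern.** A significance test of a difference takes no difference as its null hypothesis. Failing to reject that null does not show that the drugs are close: a small or noisy trial also fails to reject. An equivalence claim needs a margin, and an interval for the treatment difference that excludes values beyond it. Read as significance tests, the stated analyses therefore do not address the stated hypothesis.

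The t-test does yield a confidence interval that could be set against 2 points, but the plan does not prespecify this. Nor does it say how a non-significant result will be read. In an open-label trial, a margin, confidence level or decision rule chosen once the data are known would be hard to defend, and the choice could change the primary conclusion.

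**Working it through.** **Inputs from the documents:** difference 2 NRS points, SD 3.0, alpha 0.05, power 80% and 40 per group (Sample Size); 45 enrolled per group. **Assumed, not in the documents:** ±2 as the margin, 0.05 for each one-sided test, the true differences, and SDs other than 3.0.

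**1. Which test gives 40 per group?**

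- Difference test, two-sided 0.05: n = 2 × [SD × (z₀.₉₇₅ + z₀.₈₀) / 2]² = 2 × [3 × (1.960 + 0.842) / 2]² = 35.3, so 36. The t-based solution is 36.3, so 37. At 40 per group the power would be 83.8%.
- TOST at ±2, 0.05 per side, true difference 0: n = 2 × [SD × (z₀.₉₅ + z₀.₉₀) / 2]² = 2 × [3 × (1.645 + 1.282) / 2]² = 38.5, so 39. The t-based calculation gives power 79.7% at 39 and 81.0% at 40, so 40.
- Enrolment: 40 / (1 − 0.10) = 44.4, so 45. No loss rate is stated; 40 of 45 implies 11.1%.

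The plan's 40 matches TOST and not a two-sided difference test. The documents name no formula, so the match does not prove that TOST was used.

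**2. Where do the two readings part?** Standard error = 3 × √(2/n), at an observed SD of 3.

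| | 40 per arm | 45 per arm |
|---|---|---|
| Standard error | 0.671 | 0.632 |
| Smallest significant observed difference | 1.336 | 1.257 |
| Half-width of 90% CI | 1.117 | 1.051 |
| 90% CI within ±2 if observed difference is below | 2 − 1.117 = 0.883 | 2 − 1.051 = 0.949 |
| Non-significant, but CI passes 2 | 0.88 to 1.34 | 0.95 to 1.26 |

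**3. How often does a trial land in that gap?** Probability of a non-significant t-test whose 90% CI is not within ±2, SD 3, by simulation:

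- True difference 0: 14% at 40 per arm, 9% at 45.
- True difference 1: 26% and 19%. At 40 per arm, 69% of trials are non-significant and 43% have a 90% CI within ±2. At 45 per arm the figures are 65% and 47%.

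**4. What if non-significance is read as similarity?** Probability of a non-significant t-test when the true difference is exactly 2 (noncentral t; noncentrality 2 / 0.671 = 2.98 at 40 per arm with SD 3). TOST at ±2 wrongly concludes equivalence 5% of the time throughout.

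| SD | 40 per arm | 45 per arm |
|---|---|---|
| 2.5 | 6% | 4% |
| 3.0 | 16% | 12% |
| 3.5 | 29% | 24% |

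There is no inflation over 5% below an SD of about 2.45 (40 per arm) or 2.60 (45 per arm).

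**5. Is the planned size enough for an explicit rule?** Base case: ±2, 90% CI, SD 3.0, true difference 0. Each later row changes one input. The last column takes all 45 as evaluable.

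| Case | n per group for 80% power | Power at 40 | Power at 45 |
|---|---|---|---|
| Base | 40 | 81.0% | 86.5% |
| 95% CI | 49 | 67.5% | 75.7% |
| True difference 0.5 | 51 | 69.6% | 74.9% |
| SD 3.5 | 54 | 62.6% | 70.4% |
| Margin ±1.5 | 70 | 43.3% | 52.1% |
| Margin ±1.0 | 155 | 0.5% | 1.6% |

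**The case against.** The strongest reply is that the margin is unlabelled rather than absent. The declared design, the hypothesis of similarity, the 2 points tied to the primary outcome, and a sample size that fits TOST better than a difference test all point one way. This is a fair inference, and it makes the repair cheap. It does not supply the rule: with ±2 granted, the confidence level and decision criterion are still unstated, and a 95% CI in place of a 90% CI moves the power at 40 from 81% to 68%. The Sample Size label for the 2 points is also difference-test language.

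Three further points have weight.

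- The 16% against 5% comparison holds only if a non-significant result is read as similarity, which the plan does not say. It also shrinks or disappears at a smaller SD.
- The 14% and 9% of trials in the gap when the drugs are identical are not errors the fix would remove. They are most of the ordinary TOST failure rate. The rule only settles that such trials are inconclusive.
- The equivalence label appears once, and the title and objective speak only of comparison, so the sponsor could drop the label. That is possible, but the hypothesis would then have to change as well.

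None of these replies locates a margin designation or a decision rule in the documents.

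**Conclusion.** The concern holds. The plan declares equivalence, but as written its pain-score analyses cannot establish it: no margin is designated and no decision rule is given. The sample size is not shown to be wrong.

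With ±2 as the margin and SD 3, the unresolved zone is an observed difference of 0.88 to 1.34 points at 40 per arm (0.95 to 1.26 at 45). If non-significance were taken as similarity, the chance of passing a true 2-point difference would exceed TOST's 5% by about 11 percentage points at 40 per arm and 7 at 45. Both results rest on a margin that the plan does not state, and the second also on a reading that it does not state. The omission itself depends on neither.

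**What to change.** In Data Analysis, insert as the primary analysis:

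> Equivalence is concluded only if the 90% CI for the AOK minus Nurtec difference in [one named 60-minute pain outcome] lies wholly within −2 to +2 NRS points (two one-sided tests, 0.05 per side). A non-significant difference test is not evidence of equivalence.

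The ±2 is borrowed from the plan's own clinically meaningful difference. The sponsor must justify it as a margin or name another. The 90% CI is one reading of the stated alpha; if a 95% CI is preferred, the text should say so. The 60-minute outcome should be named identically in Hypothesis, Data Analysis and Expected Outcomes, with the 120-minute tests, other t-tests and mixed model labelled secondary.

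In Sample Size, state the basis:

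> 40 evaluable patients per group give about 81% power for two one-sided tests at ±2 points, 0.05 per side, SD 3.0 and a true difference of 0.

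Give beside it the power under less favourable inputs: about 70% at a true difference of 0.5, 63% at SD 3.5, or 68% with a 95% CI.

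**Cost.** On the base inputs this is wording only: 40 are needed and 45 are planned. With a 95% CI, a true difference of 0.5 or SD 3.5, the planned 45 falls short of 80% power, and the text should report the power actually available. A tighter margin is costlier: ±1.5 would need 70 per group and ±1.0 would need 155. Under ±1.0, restating the power at about 2% would not rescue the trial, and the sponsor would have to decide whether to resource it. The price of the rule is that a trial whose interval is too wide must be reported as inconclusive.

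### The primary outcome is defined both as the 60-minute score and as the reduction from baseline, with no primary analysis named; one baseline-adjusted model would serve both definitions

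*Combined protocol and SAP*

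**What the plan says.** Three places describe the primary outcome, and they differ.

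- **Hypothesis:** the between-group difference in "pain scores at 60 minutes post-medication administration".
- **Expected Outcomes** puts it this way: "The primary outcome will include a comparative reduction of pain scores on numeric rating pain scale (NRS) at 60 minutes from the baseline". That section lists "change in pain score up to 120 minutes" as secondary.
- **Data Analysis:** a primary outcome built on "a minimal clinically meaningful difference of 2 points between two groups at the 60-minute and 120-minute pain assessment".

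For methods, Data Analysis lists an "independent-sample t-test to assess differences in pain scores at the various intervals". Its next sentence reads: "Mixed-model linear regression will be used to compare changes in pain numeric rating scale across time points". Neither is designated primary, no covariate is named, and nothing says how baseline enters the mixed model. Data Collection Procedures has the baseline NRS recorded for each patient.

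Sample Size assumes a 2-point difference "with Standard deviation of 3.0, alpha=0.05, and power of 80" (percent), giving 40 per group and 45 enrolled. It does not say whether 3.0 is the SD of the score or of the change. The Design paragraph calls the trial an open-label equivalence trial, but the 2 points are nowhere labelled a margin.

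The entry score also differs: at least 5 under Study Design (Subjects), and 5 under Eligibility Criteria.

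**The concern.** Score and change are different variables with different SDs. Their unadjusted treatment estimates differ by exactly the chance imbalance in baseline NRS. One data set can therefore meet an equivalence criterion on one definition and fail it on the other. Nothing in the plan says which result counts, and staff know the allocation. A third route, adjusting for the recorded baseline, is not mentioned, although it would make the choice between score and change irrelevant.

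The planning SD raises a related question. If 3.0 belongs to one variable and the other is analysed without adjustment, the stated power need not apply.

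**Working it through.** **Inputs.** From Sample Size: difference 2, SD 3.0, alpha 0.05, power 80%, 40 per group. Not in the documents, so assumed: the 2 points act as a margin of ±2, the decision uses a 90% interval (two one-sided tests at 0.05), there is no true difference, data are normal, baseline SD *s_b* is 1.2 to 1.7, and the baseline-to-60-minute correlation ρ is 0 to 0.5.

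**Step 1. The plan's own figure.** A superiority calculation gives 36 per group two-sided, or 28 one-sided, not 40. The equivalence reading does give 40:
- Normal approximation: n = 2 × [3 × (1.645 + 1.282)/2]² = 38.5, so 39.
- t-based: power 0.797 at 39 and 0.810 at 40, so 40.
- Loss to follow-up of 10% (the rate is not stated): 40/0.90 = 44.4, so 45.

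A margin of 2 is therefore a fair working reading.

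**Step 2. Why the adjusted model settles score versus change.** If Y60 = a + b·arm + c·B + e, then Y60 − B = a + b·arm + (c − 1)·B + e. The arm coefficient b and residual e are unchanged, so estimate, standard error, interval and p-value are identical. In one simulated data set (40 per arm), both adjusted fits gave −1.4735 (SE 0.4996). The unadjusted estimates were −1.60 for score and −1.35 for change. The gap of −0.25 is the baseline imbalance.

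**Step 3. Conflicting decisions, score SD 3.0.** The table shows the share of 20,000 simulated trials per setting in which the unadjusted score and change comparisons disagree on equivalence:

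| ρ | 0 | 0.1 | 0.3 | 0.5 |
|---|---|---|---|---|
| *s_b* = 1.2 | 13.3% | 11.8% | 10.6% | 12.2% |
| *s_b* = 1.7 | 22.2% | 19.2% | 15.4% | 14.9% |

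The adjusted model never disagrees with itself, as Step 2 requires.

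**Step 4. Power and precision, score SD 3.0.**
- Unadjusted score: SE = 3 × √(2/40) = 0.671, 78 df, 90% half-width 1.665 × 0.671 = 1.12, power 81.0%.
- Adjusted: residual SD 3√(1 − ρ²), 77 df, variance factor 1 + 1/76 for estimating the slope:

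| ρ | 0 | 0.1 | 0.3 | 0.5 |
|---|---|---|---|---|
| Power | 80.3% | 80.8% | 84.8% | 91.9% |
| 90% half-width | 1.12 | 1.12 | 1.07 | 0.97 |

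Break-even with the unadjusted score is near ρ = 0.115.
- Unadjusted change: SD = √(9 + s_b² − 6ρs_b). At s_b = 1.7 and ρ = 0 this is √11.89 = 3.45, and power is 64.6%.

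**Step 5. If 3.0 is the SD of the change.** The score SD is then ρs_b + √(9 − s_b²(1 − ρ²)).
- At s_b = 1.7, ρ = 0: √6.11 = 2.47. Power is 94.8% for the unadjusted score and 94.5% adjusted.
- At s_b = 1.7, ρ = 0.5: 0.85 + √6.8325 = 3.46. Power for the unadjusted score is 64.0%. The adjusted residual SD is 3.46 × √0.75 = 3.00, with power 80.3%.
- Unadjusted change has 81.0% throughout.

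**Step 6. A floor for the adjusted model.** The residual SD is the smallest SD of Y60 − kB over all k. Score is k = 0 and change is k = 1, so under either reading it cannot exceed 3.0. Adjusted power therefore stays at or above 80.3% with 40 analysed per arm, whatever the baseline SD and correlation.

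**The case against.** The strongest reply is that this is loose wording with modest consequences.

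- **No t-test on change is planned.** Changes are assigned to the mixed model, so Step 3 compares the simplest analysis of each definition, not two named tests. That is correct. But the mixed model's interval depends on a covariance structure and a handling of baseline that the plan does not give, so the analysis of change is less determined, not more.
- **The disagreement rates overstate the harm.** They arise at zero true difference, where a split means one analysis missed a true equivalence. At a true difference of 2, each analysis alone declares equivalence in about 5% of trials, and taking whichever passes raises this to about 6% to 7%. This stands: the inflation of false equivalence is real but small.
- **Naming either definition would remove the ambiguity.** Also true. The adjusted model is preferable because it makes the choice immaterial and protects power under either reading of SD 3.0. Its gain in precision depends on a correlation the documents do not give, and entry restricted to scores of at least 5 tends to weaken that correlation.
- **The model alone does not decide equivalence.** The plan must also state a margin and an interval rule. That is a further requirement and does not argue against the model.

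If every patient entered with a score of exactly 5, baseline would be constant and score versus change would not matter. The Study Design wording does not support that reading.

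**Conclusion.** The concern holds, as something that should be corrected before analysis. The primary outcome is defined inconsistently and no primary analysis is named, while a covariate that would remove the score-versus-change conflict is already collected. The planned t-test is not invalid, and 40 per group is not shown to be too few.

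The algebraic identity and the 3.0 ceiling on the residual SD do not depend on the assumed baseline SD or correlation. The conflict rates of 10.6% to 22.2% do depend on them, and also on the ±2 margin, the 90% interval and normal data; the model ignores the 0 and 10 limits of the scale. An unadjusted analysis that does not match the planning SD can fall to about 64% to 65% power under the same assumptions. The adjusted model does not settle whether the primary time point is 60 minutes alone or 60 and 120 minutes.

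**What to change.** State one primary analysis, for example:

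> The primary endpoint is the NRS pain score at 60 minutes. It will be analysed by a linear model with treatment arm and baseline NRS as covariates. The adjusted mean difference will be reported with the confidence interval on which the equivalence decision is based. Unadjusted t-tests are supportive.

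Then:
- use the same endpoint wording under Hypothesis and Expected Outcomes;
- state the equivalence margin and interval rule that this model feeds;
- specify the mixed model, for example post-baseline NRS as outcome with arm, time, arm-by-time and baseline NRS;
- say whether SD 3.0 refers to the score or the change;
- separately, reconcile the 60- and 120-minute primary wording in Data Analysis with Hypothesis and Expected Outcomes, and the entry score between Study Design and Eligibility Criteria.

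The cost is wording and one covariate already on the data sheet. It uses one degree of freedom, at worst about 0.7 percentage points of power (81.0% to 80.3%) if baseline is unrelated to the 60-minute score. No extra patients or assessments are needed.
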